5.3 Concomitant Medications

Prior and concomitant medications will be collected throughout the study and will be coded according to the latest version of the WHO Drug Reference List. The actual medication listed on the CRF along with the coded name, Anatomical Therapeutic Chemical (ATC) classes, reason, start date, stop date, dose, unit, frequency, route and a flag for prior/concomitant status will be listed. The prior/concomitant flag will be identified using the end date of the medication; if the end date is prior to the start of study treatment then the medication is defined as prior, otherwise it is concomitant. Partial end dates will be imputed and flagged in the listing. Details are provided in RAP Module 8.1. A frequency tabulation for the concomitant medications will be presented for each of the ATC levels and coded medications for both core phase and extension phase analyses. This will be based on the full analysis set. Table will be repeated during extension phase analyses excluding patients missing Safety Follow-up assessments during Extension study phase.

5.4 Study Medication

5.4.1 Dose reductions or interruptions

Exposure to study treatment, relative dose intensity, dose reductions and interruptions will be summarized after completion of core phase and extension phase. Dosages may be adjusted for a number of reasons, see the protocol for details.

The number of patients who have dose reductions or interruptions, the number of dose reductions or interruptions, as well as their reasons, will be summarized by treatment. This will be done for all reductions or interruptions together and then summarized just for reductions and again just for interruptions. The number of dose reductions/interruptions will be the sum of the number of reductions and the number of interruptions. A patient who reduced their dose to zero will be counted only once in the dose reduction/interruption summaries, i.e. not counted once as a reduction and counted again as an interruption.

If a patient moves from a higher than protocol planned dose down to the planned dose then this is not be counted as a reduction, however if they move directly from a higher than planned dose down to a lower than protocol planned dose or the planned dose on a less frequent regimen, then this is counted as a reduction.

Everolimus

Interruption: An interruption is defined as a 0mg/0tablets dose given on one or more days or a 0mg/0tablets record entered for a weekly dosing schedule.

Reduction: A reduction is defined as a decrease in dose from the protocol planned dose or a decrease from the previous non-zero dose, even if this decrease has been directly preceded by an interruption. A decrease to zero will not be counted as a reduction. For example, in the sequence 10mg – 0mg – 5mg, only the 5mg dose will be counted as a reduction. A decrease in frequency of administration which results in a lower cumulative dose is also counted as a reduction, e.g. in the sequence 10mg od – 5mg od – 5mg qod, two reductions will be counted.

Pasireotide LAR

Interruption: An interruption is defined as a 0mg dose entered for a monthly dosing schedule or the time between two Pasireotide LAR administrations being more than 31 days (28 days + 3 days).

Reduction: A reduction is defined as a decrease in dose from the protocol planned dose or a decrease from the previous non-zero dose, even if this decrease has been directly preceded by an interruption. A decrease to zero will not be counted as a reduction.

Combination arm

Dose reductions and interruptions will be calculated separately for both Pasireotide LAR and Everolimus treatments.

5.4.2 Duration of exposure

Everolimus

The following algorithm will be used to calculate the duration of Everolimus exposure:

Duration of exposure (weeks) = (min(date of last administration of Everolimus, date of data cut-off) – (date of first administration of Everolimus + 1)) / 7.

The duration includes the periods of temporary interruption.

Pasireotide LAR

The following algorithm will be used to calculate the duration of Pasireotide LAR exposure:

Duration of exposure (weeks) = (min(date of last administration of Pasireotide LAR +27, date of death, date of data cut-off) – date of first administration of Pasireotide LAR + 1) / 7.

Combination arm

The duration of exposure in the combination arm will be computed for the individual components separately and combined. The exposure for the individual components will be

calculated using the methods above. The duration of exposure to the study treatment for the combined treatment will be calculated as follows:

Duration of exposure (weeks) = (last date of exposure to any study treatment component – date of first administration of study treatment + 1) / 7.

With the last date of exposure to any study treatment component defined as: max (min(date of last administration of Pasireotide LAR +27, date of death, data cut-off date) for Pasireotide LAR, min(date of last Everolimus administration, data cut-off date) for Everolimus).

Summaries of the exposure to each treatment i.e. duration (weeks) of application of study medication will be presented for the safety set.

The total number of patients who received each component will be summarized, with the combination arm being split into three (Pasireotide LAR, Everolimus and Both). Duration of study treatment exposure will be summarized with means of descriptive statistics.

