7.2.2.5.3 Biochemistry

The following tests will be performed at each scheduled visit (± 7 days during monthly visit period and ± 2 days during the weekly visit period) as indicated in [Table 7-1](#) and in [Table 7-2](#) and will include sodium, potassium, chloride, bicarbonate, creatinine, total protein, uric acid, BUN (or urea, if BUN cannot be directly evaluated), calcium, magnesium, phosphate. If the biochemistry tests of Visit 1 have been done less than 7 days before treatment start, they should not be repeated on Cycle 1 Day 1.

One pre-dose, blood draw for plasma ACTH will be taken at visit 1 (baseline). In patients with ACTH hypersecretion at baseline, ACTH will be tested during the study every 3 month (± 7 days).

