3.9.3 Missing data handling

Throughout the study reasonable attempts will be made to limit the amount of missing data. However the majority of missing data will not be imputed. The only exceptions to this are for the RECIST calculations, see the table in the Primary efficacy evaluation section and censoring for the time to analyses detailed in the secondary efficacy evaluation sections.

4 General Strategies of Data Presentation

All categorical data will be summarized by frequencies and percentages. Where categorical data is missing, a ‘Missing’ row will be included at the bottom with frequencies and percentages for it also presented.

Continuous data will be summarized with either standard descriptive statistics (i.e. the number of non-missing data points, arithmetic mean, standard deviation, minimum, median and maximum), or will be collapsed into categorical data and summarized as categorical data.

Day 1 is relative to the treatment start date and is calculated as date of interest – treatment start date + 1. For visits/events occurring prior to treatment start date the ‘+1’ will be excluded, so the day before day 1 is day -1.

5 Patient Disposition, background and demographic characteristics

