5.4.3 Relative dose intensity

Relative dose intensity (RDI) will be summarized separately for each study drug and is defined as follows:

$RDI = DI \text{ (dosing unit / unit of time)} / PDI \text{ (dosing unit / unit of time)}$.

Dose intensity (DI) is defined as follows:

$DI \text{ (dosing unit / unit of time)} = \text{Cumulative dose (dosing unit)} / \text{Duration of exposure (unit of time)}$.

For patients who did not take any drug the DI is by definition equal to zero.

For both Pasireotide LAR and Everolimus the unit of time will be weeks.

Planned dose intensity (PDI) is the assigned dose by unit of time planned to be given to patients as per protocol in the same dose unit and unit of time as that of the Dose Intensity.

$PDI = 10 \text{ mg/day} = 70 \text{ mg/week}$ for Everolimus.

$PDI = 60\text{mg per 28 days} = 15 \text{ mg/week}$ for Pasireotide LAR.

In the combination arm, RDI will be summarized separately for each component, but using the duration of the study treatment exposure, not the duration of each of the components.

Cumulative dose is defined as the total dose taken by the patient during the study treatment exposure and will be summarized for each of the study treatment separately.

For Everolimus total dose = sum of all rows on the dosage administration record of (actual dose * (date of end of medication – date of start of medication + 1 (only '+1' if end date not the same as the start date of the next dose))). If the date of end of medication is missing or after the cut-off date then the cut-off date will be used instead. Note that actual dose is the daily dose a patient has taken, if a dose is taken every other day instead then the daily dose will be halved.

For Pasireotide LAR total dose = sum of all doses recorded on the dosage administration record CRF page.

Mean and median relative dose intensity will be displayed along with exposure summaries. Summary of actual dose intensity, categories of relative dose intensity (<70%, 70 - <90%, 90 - <100% and >=100%) and cumulative dose received summary will be displayed in a separate table.

6 Efficacy evaluation

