10.2 Laboratory values

All laboratory values will be converted into SI units; for laboratory tests covered by the CTCAE version 4.0 (see National Cancer Institute (NCI) 2009), the study's biostatistical and reporting team will grade laboratory data accordingly. For laboratory tests covered by CTCAE, a Grade 0 will be assigned for all non-missing values not graded as 1 or higher. Grade 5 will not be used. For laboratory tests where grades are not defined by CTCAE, results will be graded by the low/normal/high classifications based on laboratory normal ranges.

All summaries will be produced separately for each lab category (hematology, biochemistry and urinalysis). Hematology includes hemoglobin, hematocrit, platelets and total white blood cell count (WBC, absolute & differential including neutrophils, lymphocytes, monocytes, eosinophils and basophils). Biochemistry includes sodium, potassium, chloride, bicarbonate, creatinine, total protein, uric acid, blood urea nitrogen (BUN), calcium, magnesium and phosphate. Urinalysis includes pH, protein, glucose, blood, ketones and leukocytes. They will be tested using a dipstick. In some cases urea results will be collected rather than BUN. In these cases urea will be converted to BUN using the following conversions:

$$\text{BUN (mg/dL)} = \text{Urea (mg/dL)} / 2.14$$

$$\text{BUN (mmol/L)} = \text{Urea (mmol/L)} / 2$$

Shift tables using CTCAE grades will be produced for hematology and biochemistry separately to compare baseline and the worst on-treatment value with each laboratory parameter on a new page. Percentages will be calculated using the number of available patients at baseline with corresponding grade and at least one non-missing post baseline value as the denominator.

For laboratory tests where CTCAE grades are not defined, shift tables using the low/normal/high/(low and high) classification will be produced to compare baseline to the worst on-treatment value with each laboratory parameter on a new page. Percentages will be calculated using the number of available patients at baseline with corresponding level and at least one non-missing post baseline value as the denominator.

The following rules will be applied to derive the WBC differential counts when only percentages are available (this is mainly important for neutrophils and lymphocytes, as the CTC grading is based on the absolute counts).

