The method to convert the value is as follows: for each patient, the original laboratory value (%) is divided by 100 and multiplied by the WBC count, e.g. for neutrophils (NEU):

NEU count = (WBC count) * (NEU %value / 100)

In order to derive the corresponding absolute normal range, the rule to be applied depends on the availability of the % range and the absolute range for the differential:

- If the % range is missing and the absolute range is missing, then the pre-defined normal range as reported in the Merck manual (FRM-0015557 Laboratory value references) will be used.
- If the absolute range is NOT missing (% range is or isn't missing), then the absolute range provided by the site will be used.
- If the % range is NOT missing and the absolute range is missing, then the % normal limits (i.e. lower limit normal (LLN) and upper limit normal (ULN)) are divided by 100 and multiplied by the corresponding normal limits of WBC count, e.g. for NEU:

LLN for NEU count = (LLN for WBC count) * (LLN for NEU % value/ 100)

ULN for NEU count = (ULN for WBC count) * (ULN for NEU % value / 100)

A listing will be presented for all hematology, biochemistry and urinalysis laboratory data, with values flagged to show the corresponding CTCAE grades and the classifications relative to the laboratory normal ranges. A separate listing will be created presenting the laboratory normal ranges for the collected parameters by laboratory identification number and laboratory group.

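### Two SAP derivations are wrong as written: everolimus exposure comes out two days short, and the mmol/L urea-to-BUN rule does not agree with the mg/dL rule

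*SAP*

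**What the plan says.** **Everolimus exposure.** SAP 5.4.2 takes the earlier of the last everolimus date and the cut-off, and subtracts a bracket ending "date of first administration of Everolimus + 1)) / 7". The pasireotide LAR formula in the same section ends "date of first administration of Pasireotide LAR + 1) / 7", with the +1 added to the difference. The formula for combined treatment in the combination arm has the same form. Interruptions are not removed from the everolimus duration.

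SAP Section 4 also counts inclusively: "Day 1 is relative to the treatment start date and is calculated as date of interest" minus the treatment start date, plus 1. SAP 5.4.3 sums everolimus dose over end − start + 1 days per record, with the qualifier "only '+1' if end date not the same as the start date of the next dose", which prevents a day being counted twice. RDI is then tabulated in "categories of relative dose intensity (<70%, 70 - <90%, 90 - <100% and >=100"%).

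**Urea to BUN.** Protocol 7.2.2.5.3 lists "BUN (or urea, if BUN cannot be directly evaluated") among the biochemistry tests. SAP 10.2 says "In these cases urea will be converted to BUN using the following conversions" and gives two: division by 2.14 for mg/dL and division by 2 for mmol/L. For white-cell differentials reported as percentages, the same section also converts the reference limits, for example "LLN for NEU count = (LLN for WBC count) * (LLN for NEU % value/ 100"). It gives no such rule for converted urea.

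**The concern.** The everolimus brackets balance, so a programmer can implement the line literally. Doing so subtracts a day where the other formulas add one. The numerator of monotherapy RDI is a dose summed over D inclusive days, while the denominator covers D − 2 days. RDI then exceeds 100% for a patient who took exactly the planned dose. The top class starts at exactly 100%, so that is where most of the misclassification would occur.

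For BUN, a sample reported in mmol/L would be listed on a different scale from a directly measured BUN. SAP 10.2 converts all laboratory values to SI units, so the mmol/L line will be used. If the reference limits are not scaled with the value, any low/normal/high shift for those patients is wrong as well. If they are scaled, only the listed values are wrong.

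**Working it through.** **Planned dose intensity (SAP 5.4.3).** Everolimus: 10 mg/day × 7 = 70 mg/week. Pasireotide LAR: 60 mg / 28 days × 7 = 15 mg/week. Both stated figures reproduce.

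**Everolimus monotherapy.** Let D be the days from first to last dose inclusive, so last − first = D − 1, and let m be the number of missed days.

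- SAP duration: (last − first − 1)/7 = (D − 2)/7 weeks.
- Inclusive duration: (last − first + 1)/7 = D/7 weeks.
- Cumulative dose at 10 mg/day: 10(D − m) mg.
- RDI under the SAP text: [10(D − m) / ((D − 2)/7)] / 70 = (D − m)/(D − 2).
- RDI under the inclusive count: (D − m)/D.

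| D | m | Inclusive RDI | RDI as written |
|---|---|---|---|
| 28 | 0 | 100% | 28/26 = 107.7% |
| 85 | 0 | 100% | 85/83 = 102.4% |
| 169 | 0 | 100% | 169/167 = 101.2% |
| 365 | 0 | 100% | 365/363 = 100.6% |
| 85 | 1 | 84/85 = 98.8% | 84/83 = 101.2% |
| 85 | 2 | 83/85 = 97.6% | 83/83 = 100.0% |
| 365 | 1 | 364/365 = 99.7% | 364/363 = 100.3% |
| 365 | 2 | 363/365 = 99.5% | 363/363 = 100.0% |
| 28 | 4 | 24/28 = 85.7% | 24/26 = 92.3% |
| 85 | 10 | 75/85 = 88.2% | 75/83 = 90.4% |

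For any D above 2, m = 1 or 2 gives (D − m)/(D − 2) of at least 1, so these patients reach the top class whatever their exposure length. The last two rows cross the 90% boundary. With D = 2 the duration is 0 weeks and RDI is undefined; with D = 1 the duration is −1/7 week.

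**Combination arm.** SAP 5.4.3 divides by the duration of combined treatment, which is inclusive, so RDI is not inflated. The separately reported everolimus component duration is still two days short.

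**Urea to BUN.** The documents give no molar masses, so I assume urea 60.06 and nitrogen 14.007 g/mol. Urea carries two nitrogens (28.01 g/mol), and 60.06/28.01 = 2.144, which reproduces the SAP's 2.14.

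Take urea at 10 mmol/L:

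- In mass units: 10 × 60.06 / 10 = 60.06 mg/dL.
- By the mg/dL rule: 60.06/2.14 = 28.07 mg/dL BUN.
- Back to mmol/L as urea nitrogen: 28.07 × 10 / 28.01 = 10.0.
- Back to mmol/L as nitrogen atoms: 28.07 × 10 / 14.007 = 20.0.
- By the SAP mmol/L rule: 10/2 = 5.0.

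The SAP mmol/L result is too low by a factor of 10.0/5.0 = 2 or 20.0/5.0 = 4. The consistent multiplier is 1 or 2, not 1/2. For the two lines to agree, BUN would need a molar mass of (60.06/2.14)/0.5 = 56.1 g/mol, which matches neither 28.01 nor 14.007.

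**The case against.** The intended everolimus count is obvious from the neighbouring formulas, and the programmed code may already be right. The documents do not show the code, so the RDI figures above are what the text produces, not demonstrated output errors. That stands, and it is why the fix includes a code check.

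The effect is also small for most patients: 0.6% at one year and 2.4% at 85 days. The larger figures need short exposure or a patient near a class edge, and nothing in the documents shows that one- or two-day exposures occurred. Duration itself is only described by summary statistics.

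RDI is in any case a rough comparison across arms. In the combination arm the denominator can run to the last pasireotide date plus 27 days. If both drugs are last given on day 85, with no death or cut-off intervening, full-dose everolimus scores 85/112 = 75.9%. That is a stated convention with a larger effect than two days, but it does not justify subtracting a day from everolimus alone.

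On BUN, different factors in different units are not inconsistent on their face; the conflict appears only once molar masses are brought in. That is correct, and the point is conditional on them. They are physical constants that return the SAP's own 2.14, and the conclusion is the same under either meaning of BUN in mmol/L. The SAP's silence on urea limits does not show that they are left unscaled, so misclassified shifts are a possibility and not a finding.

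**Conclusion.** Both lines are wrong as written. The everolimus duration is two days short for every patient whose exposure is computed from the text. Monotherapy RDI is overstated by a factor of D/(D − 2), and one or two missed days still count as 100% or more. The effect is slight at long exposure and matters mainly for early stoppers and at class boundaries. Combination-arm RDI is not inflated.

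The mmol/L BUN rule gives values 2 to 4 times too low relative to the mg/dL rule, given the assumed molar masses. It concerns only sites that report urea, whose number is not given.

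Neither error touches the primary endpoint, the Fleming decision rule or the safety parameters that Protocol Section 10 names for choosing among arms. The consequence is confined to descriptive exposure and laboratory outputs, but the correction costs so little that it should be made.

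**What to change.** - **SAP 5.4.2:** define everolimus duration in weeks as (min(last everolimus date, cut-off) − first everolimus date + 1)/7. Full-dose monotherapy RDI is then D/D = 100% at every D.
- **SAP 10.2:** replace the mmol/L line with BUN (mmol/L, expressed as urea nitrogen) = urea (mmol/L), and state that the laboratory's urea limits are carried over with the same factor. Alternatively, keep urea as its own parameter and classify it against the laboratory's urea range, which avoids choosing a convention for BUN in mmol/L.
- **Code:** check what was programmed for both derivations. Re-run the exposure, RDI and BUN outputs only if the code followed the text.

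The cost is two lines, one sentence on limits and a code check. No new data are needed.

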5.4.3 Relative dose intensity

Relative dose intensity (RDI) will be summarized separately for each study drug and is defined as follows:

$RDI = DI \text{ (dosing unit / unit of time)} / PDI \text{ (dosing unit / unit of time)}$.

Dose intensity (DI) is defined as follows:

$DI \text{ (dosing unit / unit of time)} = \text{Cumulative dose (dosing unit)} / \text{Duration of exposure (unit of time)}$.

For patients who did not take any drug the DI is by definition equal to zero.

For both Pasireotide LAR and Everolimus the unit of time will be weeks.

Planned dose intensity (PDI) is the assigned dose by unit of time planned to be given to patients as per protocol in the same dose unit and unit of time as that of the Dose Intensity.

$PDI = 10 \text{ mg/day} = 70 \text{ mg/week}$ for Everolimus.

$PDI = 60\text{mg per 28 days} = 15 \text{ mg/week}$ for Pasireotide LAR.

In the combination arm, RDI will be summarized separately for each component, but using the duration of the study treatment exposure, not the duration of each of the components.

Cumulative dose is defined as the total dose taken by the patient during the study treatment exposure and will be summarized for each of the study treatment separately.

For Everolimus total dose = sum of all rows on the dosage administration record of (actual dose * (date of end of medication – date of start of medication + 1 (only '+1' if end date not the same as the start date of the next dose))). If the date of end of medication is missing or after the cut-off date then the cut-off date will be used instead. Note that actual dose is the daily dose a patient has taken, if a dose is taken every other day instead then the daily dose will be halved.

For Pasireotide LAR total dose = sum of all doses recorded on the dosage administration record CRF page.

Mean and median relative dose intensity will be displayed along with exposure summaries. Summary of actual dose intensity, categories of relative dose intensity (<70%, 70 - <90%, 90 - <100% and >=100%) and cumulative dose received summary will be displayed in a separate table.

6 Efficacy evaluation

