- If grade 3 hyperglycemia (>250 mg/dL; >13.9 mmol/L) persists despite interruption of pasireotide LAR treatment (≥ 56 days from last injection) and despite optimal antidiabetic treatment, the dose of everolimus should also be interrupted, i.e. this patient should be discontinued from the study (Table 6-1).

Table 6-1 Dosing modification for hyperglycemia

CTCAE grade	Pasireotide LAR monotherapy arm	Everolimus monotherapy arm	Everolimus and pasireotide LAR combination arm
Grade ≤ 2 (≤250 mg/dL; ≤13.9 mmol/L)	No dose adjustment necessary. Consider start or adjustment of antidiabetic therapy.	No dose adjustment necessary. Consider start or adjustment of antidiabetic therapy.	No dose adjustment necessary. Consider start or adjustment of antidiabetic therapy.
Grade ≥ 3 (>250 mg/dL; >13.9 mmol/L)	Interrupt pasireotide LAR until recovery to grade ≤ 1 Optimize antidiabetic therapy. - If hyperglycemia recovers to grade ≤ 1, reinstate pasireotide LAR at the lowest dose level (20 mg). If hyperglycemia is well controlled, the dose of pasireotide LAR can be escalated in steps to the original dose with the appropriate monitoring of blood glucose levels. - If grade ≥3 hyperglycemia (>250 mg/dL; >13.9 mmol/L) persists despite interruption of pasireotide LAR treatment (≥56 days from last injection) and despite optimal antidiabetic treatment, the patient should be discontinued from the study	Interrupt everolimus until recovery to grade ≤ 1 Optimize antidiabetic therapy. - If hyperglycemia recovers to grade ≤ 1, reintroduce everolimus at one dose level lower. - If grade 3 hyperglycemia (>250 mg/dL; >13.9 mmol/L) persists despite interruption of everolimus treatment (≥28 days from last dose) and in spite of optimal antidiabetic treatment, the patient should be discontinued from the study	Interrupt pasireotide LAR until recovery to grade ≤ 1 Optimize antidiabetic therapy. - If hyperglycemia recovers to grade ≤ 1 reinstate pasireotide LAR at the lowest dose level (20 mg). If hyperglycemia is well controlled, the dose of pasireotide LAR can be escalated in steps to the original dose with the appropriate monitoring of blood glucose levels. - If grade ≥3 hyperglycemia (>250 mg/dL; >13.9 mmol/L) persists despite interruption of pasireotide LAR treatment (≥56 days from last injection) and despite optimal antidiabetic treatment, interrupt everolimus and discontinue the patient from the study.

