6.3.2 Treatment interruption and treatment discontinuation

Patients experiencing unacceptable toxicity (AE of grade 3 or higher, including laboratory value changes of grade 3 or higher) that the investigator considers directly attributable to the study drugs should have their dose reduced or be withdrawn from the study. [Section 6.3.1.1](#) and [Section 6.3.1.2](#) should be regarded as a guideline for the treatment of patients

experiencing adverse events which are judged to be drug-related. Any deviation from these guidelines should be discussed and approved by the sponsor.

For patients treated in the pasireotide LAR monotherapy arm or in the combination arm, in case the re-escalation from 20 to 40 mg of pasireotide LAR is not possible due to toxicity issues, the patient will be discontinued (Table 6-9). For patients treated in the combination arm, the patient will be maintained on study treatment unless the 20 mg pasireotide LAR dose cannot be re-escalated (Table 6-9). If one drug of the combination is discontinued, the combination treatment will be discontinued.

Table 6-9 Recommendations for patient discontinuation following study drug adjustment

Dose levels reached after tolerability issues	Action
Pasireotide LAR 20 mg	If re-escalation to 40 mg* is not possible, the patient will be discontinued and followed for safety
Pasireotide LAR 40 mg	Patient can be maintained on study treatment
Pasireotide LAR 20 mg and everolimus 5 mg e.o.d.	If re-escalation of pasireotide LAR to 40 mg* is not possible, the patient will be discontinued and followed for safety
Pasireotide LAR 40 mg and everolimus 5 mg e.o.d.	Patient can be maintained on study treatment
Pasireotide LAR 60 mg and everolimus 5 mg e.o.d	Patient can be maintained on study treatment
Pasireotide LAR 20 mg and everolimus 5 mg daily	If re-escalation of pasireotide LAR to 40 mg* is not possible, the patient will be discontinued and followed for safety
Pasireotide LAR 40 mg and everolimus 5 mg daily	Patient can be maintained on study treatment
Pasireotide LAR 60 mg and everolimus 5 mg daily	Patient can be maintained on study treatment
Pasireotide LAR 20 mg and everolimus 10 mg daily	If re-escalation of pasireotide LAR to 40 mg is not possible, the patient can not be maintained on study treatment
Pasireotide LAR 40 mg and everolimus 10 mg daily	Patient can be maintained on study treatment

[figure not shown]
* Re-escalation of pasireotide LAR from 20 to 40 mg has to be performed within 56 days.

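### Relative dose intensity in the combination arm uses the joint treatment duration, so the same dosing history can score lower there than in monotherapy, and never higher

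*SAP*

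**What the plan says.** SAP 5.4.3 defines dose intensity as cumulative dose over duration of exposure in weeks. RDI is that figure divided by the planned intensity: 70 mg/week for everolimus and 15 mg/week for pasireotide LAR. SAP 5.4.2 gives the durations:

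- **Everolimus:** "min(date of last administration of Everolimus, date of data cut-off) – (date of first administration of Everolimus + 1)) / 7".
- **Pasireotide LAR:** from the first injection to "min(date of last administration of Pasireotide LAR +27, date of death, date of data cut-off", counted inclusively.
- **Combination:** from first study treatment to the later of the two component end dates. The pasireotide part of that rule is "max (min(date of last administration of Pasireotide LAR +27, date of death, data cut-off date) for Pasireotide LAR"; the other part is the last everolimus dose or the cut-off.

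SAP 5.4.2 also computes each component's own duration in the combination arm. SAP 5.4.3 does not use it: component RDI there is obtained "but using the duration of the study treatment exposure, not the duration of each of the components". Neither document gives a reason, and no RDI on component duration is planned beside it. Mean and median RDI appear with the exposure summaries, and a separate table uses the categories <70%, 70 to <90%, 90 to <100% and >=100%. SAP 5.4.1 has RDI summarised after the core phase and again after the extension phase.

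**The concern.** A reader of these tables will compare everolimus with everolimus and pasireotide with pasireotide across arms. The denominators differ, and the joint duration can never be shorter than a component's own. Two situations matter.

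1. **Everolimus tail.** If both drugs stop mid-cycle, the combination denominator can run up to 27 days past the last injection, including days after everolimus has ended when no tablets were due.
2. **Terminal pasireotide hold.** Protocol 6.1.4.5.2 interrupts pasireotide for grade 3 or higher hyperglycemia in the combination arm. Only if the event persists at least 56 days from the last injection does it say that "the dose of everolimus should also be interrupted, i.e. this patient should be discontinued from the study". The time on everolimus alone lowers pasireotide RDI in the combination arm. The same terminal hold is not counted in the pasireotide arm.

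At stake is whether a difference in the RDI tables reflects dosing or the formula. The top category starts at 100%, so even a short tail moves a fully compliant patient out of it.

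**Working it through.** **Plan's own figures.** 10 mg × 7 = 70 mg/week and 60 mg / 28 × 7 = 15 mg/week. Both match SAP 5.4.3.

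**Formula.** RDI = (cumulative dose / weeks) / planned intensity. With Day 1 as first dose, everolimus at 10 mg daily to Day D and last injection on Day L:

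- Monotherapy everolimus on inclusive days: 10D / (D/7) / 70 = 100%.
- Combination, no cut-off cap: D / max(D, L+27).
- Combination, cut-off on Day C at or after D: D / max(D, min(L+27, C)).

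Because the denominator is a maximum, the combination value can equal the own-duration value or fall below it, never exceed it.

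**Everolimus, full dose, both drugs stopped on Day D**

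| Stop day D | Last injection L | Combination, uncapped | Cut-off at D+7 (assumption) |
|---|---|---|---|
| 58 | 57 | 58/84 = 69.0% | 58/65 = 89.2% |
| 64 | 57 | 64/84 = 76.2% | 64/71 = 90.1% |
| 84 | 57 | 84/84 = 100% | 100% |
| 92 | 85 | 92/112 = 82.1% | 92/99 = 92.9% |
| 364 | 337 | 364/364 = 100% | 100% |

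Averaged with equal weight over every stop day from 29 to 364, full dose, combination everolimus RDI is:

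- 91.2% uncapped (range 51.8 to 100);
- 95.7% with a cut-off 7 days after the stop (range 80.6 to 100);
- 93.0% with a cut-off 14 days after the stop;
- 100% with the cut-off on the stop day.

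The even spread of stop days is an assumption, not a figure from the documents.

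**Which cap applies.** SAP 3.4.1 sets the core cut-off at the 12-month or end-of-core evaluation, and the Protocol's Amendment 5 rationale describes it as applied per patient. Protocol 7.1.4 calls discontinuing patients in as soon as possible without fixing a day. The 7-day figure borrows the end-of-treatment window in Protocol Appendix 14.1.4.2. For the cumulative analysis, SAP 3.4.2 states no per-patient cut-off, so the uncapped column could apply there.

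**Pasireotide, terminal hold.** Injections of 60 mg on Days 1, 29 and 57 total 180 mg. Pasireotide is then held, and treatment ends on Day 113 (57 + 56).

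- Pasireotide arm: duration 57 + 27 = 84 days = 12 weeks; 180 / 12 / 15 = 100%.
- Combination arm, everolimus continued to Day 113: 180 / (113/7) / 15 = 74.3%.

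The cut-off does not remove this gap, because everolimus itself runs to Day 113. If everolimus does not outlast the last injection + 27 days, pasireotide RDI is the same in both arms.

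**Related detail.** As printed, the everolimus bracket encloses first dose + 1, giving D−2 days instead of D. Full-dose monotherapy RDI then exceeds 100% (64/62 = 103.2% at Day 64), which widens the gap slightly.

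**The case against.** The rule is explicit, and a regimen-based denominator is a legitimate choice. One-drug interruptions are built into the protocol: pasireotide alone for hyperglycemia, everolimus alone for pneumonitis and hepatitis B reactivation. A joint denominator shows how much of the two-drug regimen was delivered. On that view the 74% is informative, since no pasireotide was given after Day 57 while treatment went on; the blind spot lies in the monotherapy formula, which ignores a terminal hold. This stands in part: some of the 74% is real non-delivery, and own-duration RDI would hide it. It does not explain the everolimus tail, where a patient with no missed tablet is scored below 100%. Protocol 6.3.2 says "If one drug of the combination is discontinued, the combination treatment will be discontinued", which limits how long one drug can run alone but does not prevent the effect during an interruption.

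The cut-off cap also stands. The 76% is the uncapped value, and in the core analysis the per-patient cut-off can shrink or remove the tail.

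A reader might infer that the rule tilts the choice of best arm against the combination. The documents do not support that. Protocol Section 10 names grade 3-4 adverse events, serious adverse events and the frequency of treatment modifications as key safety parameters, and SAP 6.3.2 adds a general risk/benefit and Bayesian evaluation; neither names RDI. A reader might also take the Amendment 5 figures (43 of 124 patients completed the core phase, so 124 − 43 = 81 did not) as the number affected. They pool three arms and give no stop timing within the cycle, so they do not show prevalence.

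**Conclusion.** The point holds as one of comparability between arms, not as a contradiction in the text. For the same dosing history, component RDI in the combination arm is equal to or lower than in monotherapy. The everolimus effect ranges from none, when end dates coincide or the cut-off is the stop day, to a drop that can cross a reporting category in early mid-cycle stoppers. For the Day 64 example it is 76% uncapped and about 90% under the 7-day assumption. The pasireotide effect arises only when everolimus outlasts the last injection + 27 days; in the example it is 74% against 100%, partly formula and partly real non-delivery. Patients who reach 12 months on both drugs are almost unaffected.

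It would go too far to say that identical histories always score differently, or that the combination is made to look under-dosed throughout. RDI carries no test or decision rule, and the Month 9 progression-free result does not depend on it.

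**What to change.** In SAP 5.4.3, report each component's RDI (mean, median and categories) over that component's own duration in all arms, and name this as the line for cross-arm comparison. Keep the joint-duration RDI in the combination arm as a separate line, labelled regimen-based and not comparable with monotherapy. Apply this to both the core and the extension outputs.

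SAP 5.4.2 already derives the component durations, so the cost is a sentence in the SAP, one more row and a rerun of the exposure tables. With inclusive days (last − first + 1), the full-dose examples above give 100% in every arm; the everolimus bracket in SAP 5.4.2 should be checked at the same time. The downside is that own-duration RDI does not count a terminal one-drug hold, which the joint-duration line and the exposure rows still show.
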